SUBJECT DEMOGRAPHICS**0 unresolved comment(s)**Age level of human subjects: (i.e., 6 mths.; 2yrs., etc.) to **Study Population:**

Describe the characteristics of the subject population, including age range, gender, ethnic background and health status. Identify the criteria for inclusion and exclusion.

Provide the following information:

- A description of the subject selection criteria and rationale for selection in terms of the scientific objectives and proposed study design;
- A compelling rationale for proposed exclusion of any sex/gender or racial/ethnic group;
- Justification for the inclusion of vulnerable groups such as children, prisoners, adults with impaired consent capacity, or others who may be vulnerable to coercion or undue influence.

Please consider these resources:

[NIH Diversity Policy](#)

[FDA Diversity Guidance](#) 

Specific Aim 1:

Based on our preliminary research, we anticipate enrolling 66% of all dyads, for a total of 1120 dyads. Once a clinic crosses from standard of care to PN in the stepped-wedge design, recruitment of all eligible parent-infant dyads in that clinic will begin. Prior to postnatal hospital discharge, parents whose infants fail their newborn hearing screening test are referred to university-based, private, or OCSHCN hearing centers for follow-up testing. The referral and contact information for these parents is collected and maintained by the state EHDI program. Within one week of postnatal hospital discharge, research personnel will contact by phone each parent referred to a OCSHCN clinic in the PN condition to describe the study, screen the parent-infant dyad for eligibility, and invite eligible dyads to enroll in the study. Informed consent will be obtained including permission to access infant hearing data from EHDI.

Inclusion criteria for parent-infant dyads:

1. Infant failed a hearing screening in one or both ears before postnatal hospital discharge
2. Infant was referred for follow-up diagnostic testing at one of the 10 participating CCSHCN clinics.
3. Parent able to speak English or another language using Cyracom, telephone interpreting service.

Exclusion criteria:

1. Children and parents live outside Kentucky or who will be moving out of Kentucky within the first three months of life.

Inclusion Criteria for Patient Navigators:

1. Age 21 years or older
2. Able to speak and read English
3. Willing to complete PN training and deliver PN.

Inclusion Criteria for Patient Navigators:

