Direct costs include the cost of: PN establishment (PN recruitment and training costs), program implementation (office space, PN time, PN travel and tools, PN materials, PN supervision, staff turnover), parent time and travel (travel to seek diagnostic or PN services, time

spent receiving diagnostic services), treatment costs (costs of a rescreen or diagnostic audiology appointment), nonmedical costs (potential cost savings due to earlier identification), and non-adherence costs for the clinics (no-show appointments). Research activity costs (e.g., data collection, human subject protection training of PNs) are not included.

Indirect costs include opportunity costs of time (e.g. loss of productivity/wages) for the parent(s).

Effectiveness: The measured outcome of effectiveness to which costs will be compared is the proportion of individuals in each group who achieve diagnosis by 3 months of age. We will derive these outcome data using clinic-level non-adherence rates reported monthly by EHDI, collected in Aim 1.

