Specific Aim 2:

Patient Navigators: Baseline data collection from PNs will occur immediately following study enrollment and before PN training, administered by a trained interviewer. At the conclusion of PN training, PNs will take an examination to ensure comprehension of critical principles necessary for successful navigation. A score >80% will be required to pass the training. PNs with less than a passing score will be allowed to repeat relevant training elements and retake the examination one time; if the examination is not passed on the second round, the PN will no longer be employed in this study and a new PN will be identified. For those who pass the examination and proceed to intervention delivery, PNs will (1) audio-record 10% of PN sessions (with parent permission) to allow assessment of fidelity, (2) complete a PN fidelity checklist following each PN session, and (3) maintain process logs detailing time, travel, attendance, frequency and modes of contact with families, and other activities and expenses associated with PN delivery using provided checklists for every phone call interval, including initial call through termination. The checklists also provide opportunity for discussion of family adjustment, to establish rapport with the parent, hearing test expectations and clinic information, community resources and education on 1, 3, 6 and 12 month hearing health care. The checklists are a more comprehensive approach to the Patient Navigator Phone Call Guide and have only study numbers as identifiers on the forms. Approximately 6 months after completing PN training, PNs will complete post-test assessments and key informant interviews, administered via REDCap or by a trained interviewer. PNs will be compensated \$25 at baseline and post-test for completing the battery of assessments. In each clinic, PN will continue after the 6-month assessment time point until the end of the 2nd quarter of Y5. These data will be shared with the CAB quarterly and recommendations on additional PN training or PN modifications will be observed.

Clinic Administrators, Staff, and Providers: Approximately 6 months after crossing to the PN condition, administrators, staff, and providers from each OCSHCN clinic will participate in key informant interviews conducted by a trained interviewer and complete quantitative measures either administered via REDCap links, over the phone, or by paper form in-person. These participants will be

compensated \$25.

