Costs: Both direct and indirect costs associated with PN will be included. Costs associated with the initial newborn hearing screen will be excluded from analyses since these costs are incurred for all infants regardless of outcomes. Direct costs include the cost of: PN establishment (PN recruitment and training costs), program implementation (office space, PN time, PN travel and tools, PN materials, PN supervision, staff turnover), parent time and travel (travel to seek diagnostic or PN services, time spent receiving diagnostic services), treatment costs (costs of a rescreen or diagnostic audiology appointment), nonmedical costs (potential cost savings due to earlier identification), and non-adherence costs for the clinics (no-show appointments). Research activity costs (e.g., data collection, human subject protection training of PNs) are not included. Indirect costs include opportunity costs of time (e.g. loss of productivity/wages) for the parent(s). Cost data will be collected and monitored annually throughout the study period, for both the intervention and standard of care conditions. Unit program costs will be documented as Aims 1 and 2 are implemented and sustained over the study period. Unit costs of PN and parent participant travel will be estimated using the distance between patient and clinic address/zip code multiplied by the standard GSA standard mileage rate and adding any lodging expenses (if applicable). Unit costs of PN time and PN supervision will be estimated using logs maintained by the PNs and supervisors, applying the hourly PN pay rate (or related rate for supervisor). Parent participant time will be estimated using the average wage rate for Kentucky (estimated using average wage data from the Bureau of Labor Statistics (BLS)). Unit treatment costs will be estimated using administrative charge data from the OCSHCN, aggregated at the clinic level. Unit cost savings associated with early identification will be estimated using data from the literature. Unit costs of non-adherence will be based on costs of PN time not used but spent (which may vary if services are centralized versus local) and staff costs associated with rescheduling as documented in staff logs. Loss of productivity will be estimated using an estimate of time away from work (calculated using driving distance) and lost wages for one parent, using BLS average wage statistics. Where cost related data are tied directly to PN reporting/logs, data will be reviewed and checked monthly to ensure consistency and check validity.

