All physical copies of data collected from study participants will be kept in passcode-protected databases and lock-boxes or in the locked office of the PI. This data will be kept separate from any identifiers and will use the assigned identification number of each corresponding participant. All electronic forms of data collected will be kept on password-protected computers and in the password-protected REDCap application. Only research staff will be able to access the data, all of whom will have human subject protection training. The link file (containing both ID numbers and identifiers) for study participants will be kept on REDCap and access will only be granted to key study personnel. All subject PHI is confidential and will be protected according to the guidelines of the Health Information Portability and Accountability Act (HIPAA).

The PNs will be considered research participants (i.e., they will complete baseline and post-test quantitative research measures) in addition to being considered UK hourly employees for their time spent in training and in delivery of navigation service to parents. Prior to study participation, we will make sure all PNs understand that their responses to research measures will not affect their employment on the study, with the exception of their post-training examination score.

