- ethics review requirements for human subject protection

Please provide links or sources where possible. If the project has been or will be reviewed by a local ethics review board, attach a copy in the "Additional Information/Materials" section. You may also consult the current edition of the [International Compilation of Human Research Standards](#)

We will be utilizing Cyracom to translate the Informed Consent Form and research procedures, including navigator phone follow up and Aim 2 consent and phone questionnaire. [name], University of Kentucky Medical Center Interpreting Services manager, has recommended Cyracom to utilize for language interpreting, as they are ATA (American Translators Association) certified. Cyracom is a telephone interpreting service for any non-English language speaking individuals that allows the caller (Commission, research personnel or navigators) to speak directly to a parent utilizing a 3-way conference calling system. Cyracom is widely used in the medical setting to interpret medical information. Research can reach many different non-English speaking potential subjects and allow them to participate if desired using Cyracom in this study. Parents who desire to participate in Aim 2 portion of the study will be given the consent form in their preferred language as a short form translation that has attestation and is certified by Cyracom.

Does your study involve **HIV/AIDS research and/or screening for other reportable diseases (e.g., Hepatitis C, etc...)?**

Yes No

HIV/AIDS Research

If you have questions about what constitutes a reportable disease and/or condition in the state of Kentucky, see ORI's summary sheet: "Reporting Requirements for Diseases and Conditions in Kentucky" [[PDF](#)].

HIV/AIDS Research: There are additional IRB requirements for designing and implementing the research and for obtaining informed consent. Describe additional safeguards to minimize risk to subjects in the space provided below.

For additional information, visit the online [IRB Survival Handbook](#) to download a copy of the "Medical IRB's requirements for Protection of Human Subjects in Research Involving HIV Testing" [D65.0000] [[PDF](#)], and visit the [Office for Human Research Protections web site](#) for statements on AIDS research, or contact the Office of Research Integrity at [contact].

PI-Sponsored FDA-Regulated Research

Is this an investigator-initiated study that:

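### Aim 3 prices navigator and supervisor time at the hourly pay rate with no employer on-costs; applied as written, this understates the labour part of patient navigation (PN) programme cost.

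*Combined protocol and SAP*

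**What the plan says.** The Costs paragraph of Research Procedures, Specific Aim 3 gives a unit-cost rule for labour. Hours come from logs kept by the navigators and their supervisors, and the price comes from "applying the hourly PN pay rate (or related rate for supervisor". That paragraph and Study Design, Specific Aim 3 list the same implementation items: "program implementation (office space, PN time, PN travel and tools, PN materials, PN supervision, staff turnover". Recruitment and training of navigators are costed separately as establishment costs.

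Records, Privacy, and Confidentiality states the navigators' employment status. They are research participants "in addition to being considered UK hourly employees for their time spent in training and in delivery of navigation service to parents".

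The Objectives section sets third-party payers as the perspective and hypothesises that PN will be cost-effective against standard of care.

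On interpreters, the inclusion criteria admit a "Parent able to speak English or another language using Cyracom, telephone interpreting service", and the section on non-English-speaking subjects extends the service to navigator calls: "We will be utilizing Cyracom to translate the Informed Consent Form and research procedures, including navigator phone follow up". The cost list does not name interpreter fees. Navigators' process logs, however, must record "other activities and expenses associated with PN delivery".

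**The concern.** An hourly pay rate, read plainly, is what the worker is paid. An employer also bears costs on top of pay. The cost list is detailed enough to name office space, materials and turnover, but neither it nor the pricing rule has a place for these on-costs. An analyst following the text would leave them out.

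Navigator hours, and supervision of navigators, arise only when a clinic is in the PN condition. Leaving out part of their cost therefore does not cancel between conditions. It lowers the PN side alone, and the Aim 3 hypothesis is that PN is cost-effective. In a programme delivered mainly by telephone, labour may well be the largest item, although the documents give no cost breakdown to confirm that.

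**Working it through.** **Figures in the plan.** The documents state no pay rate, on-cost rate, logged hours, programme cost or cost-effectiveness ratio. There is no figure to reproduce, and what follows is an illustration under stated assumptions.

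**Inputs**
- Pricing rule: logged hours × hourly pay rate (Research Procedures, Specific Aim 3, Costs).
- Employer: the university, on an hourly basis (Records, Privacy, and Confidentiality).
- On-cost rate *f*, as a fraction of pay: assumed 0.08 to 0.30.
- Labour share *s*, meaning navigator and supervisor time as a fraction of PN programme cost under the rule: assumed 0.50 to 0.90.

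**Formulae.** If *C* is PN programme cost with labour at pay only, labour is *sC* and the omitted on-costs are *f × sC*. Then:
- ratio of full cost to stated cost = 1 + *sf*
- shortfall as a share of full cost = *sf* / (1 + *sf*)

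| *f* | *s* | 1 + *sf* | Rise on stated cost | Shortfall as share of full cost |
|---|---|---|---|---|
| 0.08 | 0.50 | 1 + 0.04 = 1.04 | 4% | 0.04/1.04 = 3.8% |
| 0.30 | 0.60 | 1 + 0.18 = 1.18 | 18% | 0.18/1.18 = 15.3% |
| 0.30 | 0.90 | 1 + 0.27 = 1.27 | 27% | 0.27/1.27 = 21.3% |

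If the intended rate already includes on-costs, *f* = 0 and nothing is missing.

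**From programme cost to incremental cost.** Write the incremental cost as Δ*C* = *C* + *R*, where *R* is every other cost difference between conditions (testing, parent time and travel, no-shows, savings from earlier identification). With *R* held fixed, adding on-costs raises Δ*C* by *sfC*, which is positive for any *f* above 0. So the direction for this component does not depend on the assumed rates. The proportional change in Δ*C* is *sf × C*/Δ*C*, and the documents do not give *C*/Δ*C*. The 4 to 27% therefore describes programme cost. It is not a change in the cost-effectiveness ratio.

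**Interpreter charges.** No usable estimate can be built. The documents give no language distribution, call volume or fee, and planned ethnicity counts do not measure interpreter need.

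**The case against.** The strongest reply is that the plan never says on-costs are excluded. The rate may be meant as a loaded one, the supervisor's is only a related rate, and costing detail may sit in the grant application to which the document refers. A reader might infer that PN cost is certainly understated. The documents do not support that much; they support it only if the rule is applied as written. But the text gives an explicit rule in terms of pay, and nothing in it tells the analyst to add anything.

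A second reply concerns perspective. Under a third-party payer view, the relevant cost is what a payer would be charged, and the documents do not say how PN would be financed. That is fair. However, the plan builds programme cost from inputs such as office space, supervision and turnover. On that approach labour should also enter at what it costs to employ.

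Third, a reader might infer that the whole cost-effectiveness ratio is biased in favour of PN. The documents do not show this. Treatment is valued from administrative charges, and parent travel and lost wages are counted, so if PN raises attendance these items could push PN cost up. Only the labour component has a clear direction.

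Fourth, a reader might infer that interpreter fees are left out. Absence from the list is not exclusion. The Costs paragraph begins by including both direct and indirect costs associated with PN, and the logs have an open expense category. Use of the service is also not confined to PN delivery, since it "allows the caller (Commission, research personnel or navigators) to speak directly to a parent". Interpreting for consent and questionnaires would be a research cost, which the plan rightly excludes. What remains is that Aim 3 states no rule for turning interpreter charges on navigation calls into a cost.

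**Conclusion.** The point holds in conditional form. Applied as written, the pricing rule omits employer on-costs from navigator and supervisor labour, understates that part of PN programme cost, and lowers that part of the incremental cost in favour of the Aim 3 hypothesis. The shortfall corresponds to a programme cost about 4 to 27% higher once corrected. That range rests entirely on the assumed on-cost rates and labour shares, neither of which is in the documents. The net direction of error in the full ratio is not established. The interpreter question is a gap in detail, not a demonstrated omission. The Aim 1 effectiveness analysis is unaffected.

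**What to change.** In the Costs paragraph of Research Procedures, Specific Aim 3, state that navigator and supervisor time is valued at pay plus the employer's actual on-costs, and report the pay-only result as a sensitivity analysis. If a loaded rate was always intended, one sentence saying so settles the matter. Record the rule before the Aim 3 results are known.

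As a clarification, add that interpreter charges for navigation calls count as a PN delivery cost, that those for consent and questionnaires do not, and that interpreter use under standard of care is treated by the same rule.

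The cost is small. Enrollment has ended, but this is a change at the analysis stage: the hours are logged under the existing plan, and the university as employer should hold the on-cost rate. Interpreter charges would come from invoices. No new contact with participants is needed. The downside for the sponsor is a slightly less favourable ratio.

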As the most common neonatal sensory disorder, infant hearing loss has an incidence of at least 1.7 per 1000 births. Early childhood hearing loss that is not identified and treated appropriately typically results in significant delays in language, cognitive, and social development, with profound later effects on education and employment. The economic costs of hearing loss are substantial: the overall lifetime medical, educational, and occupational costs due to deafness are estimated to be \$2.1 billion.⁴ The U.S. Preventive Services Task Force (USPSTF) reported that early detection and intervention of infant hearing loss decreases speech impairment, social/emotional challenges, and learning/behavioral disorders.⁵⁻⁷ The Joint Committee on Infant Hearing (JCIH) recommends that all infants be screened before 1 month of age, diagnosed before 3 months of age, and initiate treatment before 6 months of age (often referred to as the "1-3-6 rule"). Early infant hearing detection and intervention (EHDI) programs are coordinated on a state level and infant hearing healthcare is typically delivered in community clinics or health departments; however, non-adherence to diagnostic testing after failed newborn screening is a national problem. EHDI programs aim to have 90% of U.S. infants with failed infant hearing screens tested and diagnosed within 3 months of failed screening, but fall unacceptably short: only 40.6% meet that standard. Heightening the concern for life-long complications due to delayed diagnosis following a failed newborn screening, the outpatient diagnostic and hearing loss treatment process is complex and difficult for parents to navigate. Families of children with hearing loss are often uninformed regarding the EHDI process and lack peer support in obtaining care for their child. Similar problems in cancer care have been addressed with patient navigation (PN) programs, leading to improved adherence to recommended diagnostic testing after abnormal screening, improved patient care, and healthcare system cost savings. Patient navigators (PNs) are trained individuals who assess and mitigate personal/environmental barriers to promote healthcare adherence and improve access to care. Our recent randomized controlled trial performed in an academic setting demonstrated PN efficacy in infant hearing healthcare. This study, conducted in collaboration with the Kentucky EHDI program, demonstrated that PN decreased infant hearing testing non-adherence (7%) compared to the standard of care (38%; $p=0.005$). Our next step is to examine the effectiveness of PN when delivered in the diverse communities served by state EHDI systems. Guided by our Community Advisory Board (CAB), EHDI partners, and hearing healthcare stakeholders, we will conduct a type 1 hybrid effectiveness-implementation trial in 10 state-funded community hearing healthcare clinics, testing PN while simultaneously investigating implementation outcomes, factors influencing implementation, and cost-effectiveness.

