Specific Aim 2: Aim 2 will investigate factors associated with implementation and effectiveness outcomes across the 10 clinic sites. This aim is guided by the Consolidated Framework for Implementation Research (CFIR), using implementation constructs and outcomes recommended by Proctor et al. Sources of data for this aim will include process records as well as quantitative and qualitative data from PNs; clinic administrators, staff, and providers; and parent participants. Consistent with CFIR, we will assess PN knowledge and behaviors following completion of the PN curriculum, including intervention fidelity; PN characteristics; inner and outer setting clinic characteristics; and four key implementation outcomes: adoption, recruitment/retention, reach/penetration, and sustainability.

Specific Aim 3: Aim 3 involves incremental cost-effectiveness analyses in which net costs and net effectiveness of the intervention will be compared with that of standard of care for patients referred to OCSHCN clinics after a failed newborn hearing screen. Hypothesis: (a) PN after a failed newborn hearing screen will be cost effective compared to the standard of care from the perspective of third-party payers. We will compare net costs and effectiveness of PN compared to standard of care. Results will be expressed as a ratio of differences in observed costs to differences of observed outcomes. The perspective of this evaluation will be third party payers.

Study Design

Describe and explain the study design (e.g., observational, secondary analysis, single/double blind, parallel, crossover, deception, etc.).

- *Clinical Research:* Indicate whether subjects will be randomized and whether subjects will receive any placebo.
- *Community-Based Participatory Research:* If you are conducting [community-based participatory research \(CBPR\)](#), describe strategies for involvement of community members in the design and implementation of the study, and dissemination of results from the study.
- *Qualitative research:* Indicate ranges where flexibility is needed, if a fixed interview transcript is not available, describe interview topics including the most sensitive potential questions.

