Parent-Infant Dyads: As part of the same phone call to obtain parental informed consent, a trained research assistant will administer baseline measures of knowledge of hearing loss, self-efficacy for obtaining follow-up testing, and perceived barriers to follow-up testing. Alternatively, the parent can choose to complete the baseline measures via REDCap links. Following completion of baseline measures, parents will be contacted by the PN to initiate intervention delivery. Post-test measures will be administered by phone by a research assistant or via REDCap 16 weeks after birth – one month after the 3-month target deadline for diagnostic testing has passed. The research assistant administering post-test measures will not have access to data regarding parents' follow-up with diagnostic testing. Parent participants will be compensated \$20 for each set of completed measures (i.e., at baseline and at post-test assessment). These data will be shared with the CAB quarterly and recommendations on additional PN training or PN modifications will be observed. At no time during this study will prospective dyads be selected by examining medical records. Dyads will be referred by the various OCSHCN clinics, and not contacted by study personnel until that time. Additionally, no survey results, or interview information (if applicable), will be added to patient records and will only be held by research personnel for the time period required by the IRB before they are destroyed.

Parent-Infant Measures: Secondary effectiveness outcomes include parent participants' knowledge, self-efficacy, and barriers regarding obtaining follow-up diagnostic testing for their infant. We will also obtain EHDI data for all enrolled infants until their one-year birthday (or until data collection ends) to determine the time from birth to initial completed diagnostic assessment, number of no-show appointments, and number of rescheduled appointments. We will also collect data from EHDI to allow for control comparison of those infants who do not participate in the program to compare outcomes regarding follow-up diagnostic testing. From this control data, we will be conducting analyses looking at the impact of the COVID-19 pandemic on diagnostic testing and newborn hearing screening throughout the state of Kentucky. We will be comparing pre-COVID data with peri-COVID data. Additionally, we will look for racial & ethnic differences in the rates of follow up testing and screenings.

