
Effectiveness: The measured outcome of effectiveness to which costs will be compared is the proportion of individuals in each group who achieve diagnosis by 3 months of age. We will derive these outcome data using clinic-level non-adherence rates reported monthly by EHDI, collected in Aim 1.

Aim 1 is involving the recruitment of 1120 parent-infant dyads over the course of 4 years referred for hearing testing to Office for Children with Special Health Care Needs (OCSHCN) clinics all across the state of Kentucky. These patients are referred to those clinics from birthing hospitals at the time of birth because the child fails a newborn hearing test in the newborn nursery. This is one while the child is in the hospital but usually no more than 3-4 weeks after the child is born. Once the dyad is referred to that OCSHCN clinic, the clinic schedules them for their office visit in that clinic. The Commission staff (not any of our research personnel) ask the parent about being contacted by the research personnel and may insert a small flyer on the study that would accompany the appointment reminder if parent would like further information. If they agree to being contacted then the OCSHCN staff send the name and contact number of the dyad to our research staff to contact about participation in the study. We do not cold call anyone and we do not go through any records to identify subjects. The potential participants are given to us by our partners at the OCSHCN. We then contact them by phone and go through the verbal consent over the phone. We do ask parents for additional contact methods, such as email or other contact, such as text messaging and make contact up to 5 times to participate if parent does not answer or requests return call initially. After one phone conversation, we may try to text the parent with general information to gauge further interest in participation. The text message would recall the research personnel he or she spoke to, a brief summary of the study and to contact research personnel if interested. The text would be sent only after initial contact to verify the parent phone number is correct. We will not be going through any medical records at that OCSHCN clinic where there are going to be seen before, during, or after participation in the study. The participants provides any important medical information on the study questionnaire once informed consent is obtained. We do not have any physical contact with the proposed participants as they are likely many miles away and we do not have research personnel at the clinic. Doing the consent over the phone is the only practice way to enroll these subjects into the study in a timely manner. It is critical to do this asap because we have to involve them in the research activities within the first week or 2 after birth. If we do this by mail we will not be able to conduct this research. We will not be going through any medical records.

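### Aim 3 takes a third-party-payer perspective but prices rescreen and diagnostic visits from clinic charges, with no stated conversion to what payers pay

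*Combined protocol and SAP*

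**What the plan says.** Under Objectives, Specific Aim 3, the hypothesis is that "PN after a failed newborn hearing screen will be cost effective compared to the standard of care from the perspective of third-party payers". The method repeats the viewpoint: "The perspective of this evaluation will be third party payers". The form of the result is also fixed there: "Results will be expressed as a ratio of differences in observed costs to differences of observed outcomes". The effectiveness outcome, under Research Procedures, Specific Aim 3, is "the proportion of individuals in each group who achieve diagnosis by 3 months of age".

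The Costs paragraph of the same section defines treatment costs as rescreen or diagnostic audiology appointments and names their price source: "Unit treatment costs will be estimated using administrative charge data from the OCSHCN, aggregated at the clinic level". Other items are valued from resource use: PN and supervisor time from logs and pay rates, travel from mileage, and parent time from average wages. The list also includes parent travel and time, parents' lost wages and the clinics' cost of missed appointments.

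**The concern.** The perspective decides which costs count and at what price. For a payer, a visit costs the amount it allows or pays, and the clinic's billed amount can differ from that. The plan fixes the perspective twice and then prices visits from the provider's side. The available text describes no payment data, charge-to-payment ratio or sensitivity analysis on this price.

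The price matters because a completed test is both the outcome and a cost. Each extra test that PN produces puts one unit price into the cost difference, so an error in that price need not cancel between conditions. The ratio would then depend partly on the agency's billing schedule rather than on payer spending.

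**Working it through.** The plan states no unit charge, payment, incremental cost or ratio, so there is no figure to reproduce. The check is algebra, with illustrative values marked as such.

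**Inputs from the documents**
- Non-adherence in the team's earlier trial in an academic setting (Background): 38% under standard of care, 7% under PN. The proportions tested on time are therefore a = 0.62 and b = 0.93, and b − a = 0.31. These are used only as an illustration.
- Outcome: diagnosis by 3 months. One completed test is treated here as one diagnosis.
- Follow-up: "We will also obtain EHDI data for all enrolled infants until their one-year birthday". Tests after 3 months can therefore be observed, but no costing period is stated.

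**Inputs not in the documents (assumed, and ranged)**
- c: unit charge for a visit, left as a symbol.
- r: payer payment divided by charge.
- L: share of infants missing the deadline who are tested later within the costing period, taken as equal in both conditions.
- One visit per tested infant, and one unit price across conditions and years.

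**Step 1: extra tests per infant**

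[b + (1 − b)L] − [a + (1 − a)L] = (1 − L)(b − a)

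- L = 0: 0.93 − 0.62 = 0.31, or 31 per 100 referrals.
- L = 0.5: 0.965 − 0.81 = 0.155, or 15.5 per 100.
- L = 1: 1 − 1 = 0.

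**Step 2: visit-cost term of the ratio**

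Divide the cost of the extra tests by b − a:
- at charges: (1 − L)c
- at payments: (1 − L)rc

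The effect size cancels, so the result does not depend on the earlier trial's 31 points.

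**Step 3: error per additional timely diagnosis**

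(1 − L)c − (1 − L)rc = (1 − L)(1 − r)c

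As a share of the unit charge:

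| r (payment/charge) | L = 0 | L = 0.5 | L = 1 |
|---|---|---|---|
| 0.3 | +70% | +35% | 0 |
| 0.5 | +50% | +25% | 0 |
| 0.8 | +20% | +10% | 0 |
| 1.0 | 0 | 0 | 0 |
| 1.2 | −20% | −10% | 0 |

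A plus sign means that PN looks more costly than it is to a payer; a minus sign means less costly.

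**Step 4: the single-price assumption**

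In a stepped wedge the PN periods fall later in calendar time, and cost data are collected annually. The plan does not say that one price is held across years. If the charge schedule moves, control-period and PN-period tests carry different prices, and that difference enters the numerator even when L = 1.

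**The case against.** A reader might infer that the plan overstates the cost of PN's extra tests and so biases the ratio against PN. The documents do not support that. They give no charge and no payment for these state-funded clinics, so charges could lie above, at or below what payers pay. They also give adherence only at the 3-month deadline, with no ever-tested rate. The hypothesis concerns timing, and the Background describes families who delay as well as families who do not return. An infant tested at month 5 under standard care and at month 2 under PN generates the same visit, and its price cancels. These objections stand: direction and size are both open.

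Two further objections stand in part. The application refers to a grant submission that is not in the available text, and a conversion may be described there, so the fair statement is that none is stated here. The perspective problem is also wider than this one price, because the cost list includes parent time, travel and lost wages and the clinics' no-show costs. That means repricing visits is not enough, but it does not remove the mismatch.

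On the other side, the error vanishes through timing only if every late infant is eventually tested within the costing period. If costs were counted over the same 3 months as the outcome, later tests would fall outside it and L would in effect be zero.

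**Conclusion.** The mismatch holds: the stated rule for pricing visits does not fit the stated perspective, and no adjustment appears in the available text. Its effect on the ratio is (1 − L)(1 − r) times the unit charge per additional timely diagnosis. Over r from 0.3 to 1.2 and L from 0 to 1, that runs from 70% of the charge too high to 20% too low, and it is zero if r = 1 or L = 1. Those ranges are assumptions, as are one visit per tested infant, equal L in both conditions and a constant unit price. A dollar total would need a charge, a payment and an ever-tested rate, and the documents give none of them.

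The point concerns one component of Aim 3, plus the related question of which cost items belong in a payer analysis. It does not touch the Aim 1 effectiveness result.

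**What to change.** - Value rescreen and diagnostic visits at allowed or paid amounts, or at one payer fee schedule by procedure code. Use the same unit price in both conditions and in all years.
- If only charges can be obtained, apply a stated charge-to-payment ratio and report the incremental cost-effectiveness ratio over a range of it.
- State the period over which visits are counted, so that later tests under standard of care are treated the same way as those under PN.
- Leave parent time, travel and lost wages and clinic no-show costs out of the payer-perspective ratio, or report them separately under a broader perspective.

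This needs no new participants or procedures, which matters because enrollment has ended. The cost is a few sentences in the plan, some added analysis work, and dependence on the chosen fee schedule or ratio. Whether the agency can supply paid amounts is not stated; the fee-schedule and ratio options do not require them from the agency.
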